The primary hypothesis to be tested is that therapy with the GHRH analog tesamorelin, which augments GH secretion), will reduce hepatic lipid and visceral adipose tissue mass in patients with HIV lipodystrophy and central adiposity. The second hypothesis to be tested is the tesamorelin therapy will reduce adipose tissue inflammation and circulating pro-inflammatory markers on macrophages in these patients.

STUDY DESIGN

The CORE study is an open-label, single arm prospective study of tesamorelin therapy of patients with HIV lipodystrophy.

Enrolled subjects will have a screening visit and 6 visits - a baseline visit before starting tesamorelin, a visit at 1 month, 3 months, 6 months, 9 months and at 1 year of tesamorelin (GHRH analogue) therapy. Blood sampling for safety labs and clinical examinations will be performed at each visit. At the baseline, 6 month and 1 year visits subjects will also undergo body composition testing by total body MRI/MRS, adipose tissue biopsy, indirect calorimetry, FSIGT and additional blood sampling. Tesamorelin is being used in this study as per its FDA approved indication and dosing for treatment of HIV lipodystrophy with central adiposity. Tesamorelin, 2 mg, will be taken daily by patients by subcutaneous self-injection

Subject Inclusion Criteria:

- HIV-infected subjects with HIV lipodystrophy (HIVLD) and abdominal fat accumulation.
- Males and females
- Ages 18-65 years
- Waist Circumference (WC): 102 cm for men, 88 cm for women (ethnicities except East/South Asians) 90 cm for men, 80 cm for women (East/South Asians)
- CD4 count >100 cells/mm³.
- HIV RNA load < 400 copies/mL

- Fasting glucose <150 mg/dL
 - Patients with mild diabetes (HbA1c<7%) that is well controlled with diet and/or oral diabetic agents besides TZDs are eligible.
- Stable antiretroviral therapy for 8 weeks (any regimen).

Exclusion criteria:

- Diabetes mellitus that is not well controlled
- History of malignancy

Study procedures

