Immuno-histochemical analysis: Macrophage antigen, CD68, expressing cells fraction/sample will be calculated to determine macrophage content (94). Adipocyte size will be measured (Image-Pro Plus, Media Cybernetics, Bethesda, MD) (95) and size distribution will be quantified (96). Adipocyte count, counts of crown-like structure and other immune (T, NK) cells and fibrosis analysis will be conducted (97). Sample processing and analyses will be uniform and paired samples will be directly compared. Quantitative RT PCR will be performed on total RNA extracted from frozen AT as described (94). Relative expression values will be determined for: adipocyte-specific genes adiponectin (ADIPOQ) and leptin (LEP), proinflammatory genes (TNF,

IL6), genes of macrophage activation markers (CD11c, CD68, MCP-1, IL1- Genes associated with AT “browning” (UCP-1, DIO2, CIDEA, PGC-1, PRDM-16), and lipid metabolism, (CIDEA, PLPLA3, SCD, PIK3R1, TCF7L2). We will use control genes to normalize data (94). Samples are analyzed in labs of [name] and NYONRC AT core.

HORMONE ASSAYS: Hormones and other markers will be measured with the following assays: IGF-1 (WHO 02/254) & GH (WHO 98/574, 22kDa GH specific antibody), IDS-iSYS chemiluminescence assay; IGF-1 & GH (WHO 98/574, 22kDa & 20kDa antibody), Insulin, IGFBP-3, hsCRP - chemiluminescent immunometric (Immulite, Siemens); HbA1C, glucose, lipids (Cobas Integra, Roche); Adiponectin (total & HMW)- ELISA (Millipore); Leptin- RIA (Millipore); FFA - enzymatic colorimetric (WAKO); IL-6 & TNF -ultrasensitive ELISA R & D.

STATISTICAL PROCEDURES

The primary outcome to be examined will be change in hepatic lipid content and the secondary outcome will be change in VAT mass with tesamorelin therapy. Additional outcomes examined will be changes in relative gene expression of adipose tissue genes, change in Si, REE and changes in other hormones and markers with tesamorelin therapy.

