The general analytic approach will be to compare baseline to post-therapy parameters in each subject by paired t-test. Repeated measures ANOVA will test adipose tissue mass change over time. Correlations between variables will be tested by Pearson’s correlation. Non-normally distributed data will be log-transformed or nonparametrics used. Multiple comparisons corrections and post-hoc tests will be used. Macrophage content (% CD68 positive cell per sample) and average adipocyte cross-sectional area will be compared in HIV lipodystrophy patients adipose tissue before vs. after tesamorelin therapy by paired t-test. Adipocyte area and macrophage content will be correlated with BMI and fat mass. Correlations between gene expression data and body mass or AT mass will be compared by a nonparametric approach. Ratios of macrophage content or relative gene expression per kg AT will be compared in patients before & after treatment by appropriate t-tests. For analysis of the blood samples differences between baseline and final study visit for each marker will be compared by paired t-test. Patterns and time course of change in serum and adipose tissue inflammation will be descriptively compared. Matching serum/gene expression marker changes will be correlated.

Sample Size is based on the number of subjects needed to detect a significant decrease in hepatic lipid with tesamorelin therapy. Preliminary data from our acromegaly treatment study were used for this estimation. Sample size of 24 pairs has 88% power to detect a hepatic lipid change of 2% with a SD of 3% at $\alpha = .05$ and 12 pairs of each gender has 80% power to detect this hepatic lipid change within gender group with a within-gender SD of 2% at $\alpha = .05$ using a two-sided paired t-test.

REFERENCES

3. Stanley TL and Grinspoon SK (2012) Body composition and metabolic changes in HIV-infected patients. *The Journal of infectious diseases* 205 Suppl 3: S383-90. 3349298.

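### Liver fat is powered overall and within each gender at alpha .05, but the plan does not say how the three tests relate, which of them the promised corrections cover, or how men and women would be compared

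*Combined protocol and SAP*

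**What the plan says.** Statistical Procedures names a single primary outcome: "The primary outcome to be examined will be change in hepatic lipid content". The design has no control arm ("The CORE study is an open-label, single arm prospective study of tesamorelin therapy"), so the inference is before versus after: "The general analytic approach will be to compare baseline to post-therapy parameters in each subject by paired t-test".

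The sample-size paragraph at the end of that section gives two power statements for this outcome. The first is overall: "Sample size of 24 pairs has 88% power to detect a hepatic lipid change of 2% with a SD of 3" (per cent). The second is by gender: "12 pairs of each gender has 80% power to detect this hepatic lipid change within gender group". The inputs printed for this second statement are a standard deviation of 2% in each gender and a paired t-test, two-sided, with alpha .05.

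On multiplicity the section has one sentence: "Multiple comparisons corrections and post-hoc tests will be used". It names no method, no family of tests and no order.

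Gender is an eligibility item under Study Design (both are eligible). It does not appear in the hypotheses under Research Aims, in the list of outcomes, or in the analysis text. No test or estimate comparing change in men with change in women is described.

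**The concern.** A test that has its own sample size, SD, alpha and power looks like a planned inference. Here there are three on one outcome (all patients, men, women), and nothing says which of them decides the primary hypothesis. Two things are at stake.

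- **False-positive control.** If the overall test narrowly misses .05, nothing in the plan prevents a fall in one gender from being presented as a powered, positive result on the primary outcome.
- **Gender-specific conclusions.** With only two separate before/after p-values, the natural reading of one significant and one non-significant result is that the drug works in one gender only. That pattern is common when the true effect is the same in both, and it does not test a difference.

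**Working it through.** **Inputs**, all from the sample-size paragraph: mean change 2%; 24 pairs with SD 3% overall; 12 pairs with SD 2% per gender; two-sided paired t-test; alpha .05. No dropout rate is given and none is applied.

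**1. The plan's own power figures.** Power is from the noncentral t with df = n − 1 and noncentrality (2/SD)·√n.

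- Overall: (2/3)·√24 = 3.27, df 23, power 87.8%. The stated 88% reproduces.
- Within gender: (2/2)·√12 = 3.46, df 11, power 88.3%. The stated 80% does not reproduce.
- 80% would fit 10 pairs (80.3%), an SD of about 2.25%, or alpha .025 with 12 pairs (79.3%).

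**2. Error under no true change.** One million simulated trials with 12 men, 12 women and normal changes. The result does not depend on the SD.

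| Handling of the three tests | At least one significant |
|---|---|
| Overall test only at .05 | 5.0% |
| Two gender tests only, .05 each | 9.7% (1 − 0.95² = 9.75%) |
| All three at .05, either direction | 11.8% |
| All three at .05, false reduction only | about 6% (2.5% for the overall test alone) |
| Genders at .025, overall at .05 | 8.1% |
| Bonferroni, .05/3 each | 4.2% |
| Overall first, genders only if it passes | 5.0% |

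The 11.8% is made up of 5.0% from the overall test plus 6.8% in which a gender is significant and the overall test is not. It is below the 14.3% for three independent tests (1 − 0.95³) because the overall result is correlated with each gender's result.

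**3. Power under Bonferroni.** At .05/3 = .0167, overall power falls from 87.8% to 74.7%, and per-gender power at SD 2% from 88.3% to 72.9%.

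**4. Identical 2% fall in both genders.** With per-gender power q, P(exactly one gender significant) = 2q(1 − q).

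- SD 2%, alpha .05: 2 × 0.883 × 0.117 = 21%.
- At the printed 80% power: 2 × 0.80 × 0.20 = 32%.
- SD 2%, alpha .025: 2 × 0.793 × 0.207 = 33%.
- SD 2%, alpha .0167: 2 × 0.729 × 0.271 = 39%.
- SD 3%, alpha .05 (sensitivity): q = 55.8%, so 2 × 0.558 × 0.442 = 49%.

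The SD 3% case is worth showing because the two stated SDs do not fit one population with equal mean changes. If both describe change, an overall variance of 9 with a within-gender variance of 4 needs gender means 2·√(9 − 4) ≈ 4.5 points apart. With equal means, the overall and within-gender SDs would be about the same.

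**5. Direct comparison, 12 versus 12.** Two-sample t with df 22 and noncentrality 2/(SD·√(2/12)) for a 2-point difference. Power is about 65% at SD 2% and about 35% (0.345) at SD 3%. For 80% power the difference must be about 2.4 or 3.6 points respectively.

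**The case against.** The best defence is that the section does promise corrections, and that an alpha quoted in a power calculation is a design input, not a decision rule. This stands in part. A reader might infer that the plan's false-positive rate is 12%, but the documents do not support that: 12% is the rate only if the promise is not applied to these tests. It also counts false increases, whereas the hypothesis is a reduction, for which the figure is about 6%. What the defence cannot supply is a method, a family or an order.

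A reader might also infer that the gender tests are co-primary, or that the sponsor intends to claim success in one gender. Neither is stated. The tests appear only in the power sentence, so their status is undefined.

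The printed 80% might suggest an unstated split of alpha to .025 per gender, since that gives 79.3%. The printed alpha is .05, so a split cannot be confirmed. Even with it, the error beside an overall test at .05 would be 8.1%.

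Two further points are fair. With no stated gender hypothesis, a missing men-versus-women test is not a failure to address a declared aim; it matters only if gender results are interpreted, and powering them makes that likely. And under the planned effect, exactly one gender positive with the overall test negative is rare: 0.1% of trials at SD 2% and 2.6% at SD 3%. The false-positive concern therefore applies mainly when the drug has little or no effect.

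**Conclusion.** The concern holds as a gap in specification. The overall test is valid and its 88% power is right. What is missing is the relation between that test and the two gender tests, and any valid basis for a statement about gender.

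Each way of filling the gap from the present text has a cost: no correction leaves the error at about 12% (about 6% for a false reduction), and Bonferroni over three tests takes overall power to about 75%. No choice of alpha removes the second problem: at SD 2%, an equal effect appears in one gender only in 21% of trials at .05, and more often at stricter levels.

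These figures assume normal changes, a 12/12 split and no dropout. The 49% figure is a sensitivity case, since the stated within-gender SD is 2%. This is a worthwhile, inexpensive correction; it does not invalidate the study.

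**What to change.** Amend Statistical Procedures as follows.

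1. State that the paired test in all patients, at two-sided .05, alone decides the primary hypothesis. Name one liver-fat measure and one time point for it: Study Procedures lists both modified Dixon and ¹H-MRS, at 6 months and 1 year, and gating on an unnamed choice among these would not hold the error at 5%.
2. Make the within-gender paired tests secondary, interpreted only if the overall test is significant. Each can stay at .05. If neither gender changes, the overall null is true and the gate holds the error at 5%; if only one gender is null, its own test is at .05.
3. Base any statement about a gender difference on one comparison of change in men versus women (two-sample t-test or gender-by-time term), reported as a difference with its 95% CI.
4. Correct the 80% within-gender power, or the alpha or SD behind it, and reconcile the two SDs.
5. Say which other tests the promised corrections cover, and by what method.

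The cost is a few sentences and one extra test on data already planned. Overall power stays at 88%. Per-gender power is essentially unchanged at SD 2% (88.3% to 88.2%) and falls from 56% to about 55% at SD 3%. No within-gender claim can be made if the overall test fails. The gender comparison will be imprecise: the 95% CI half-width is about 2.07 × 2 × √(2/12) = 1.7 points at SD 2% and 2.5 points at SD 3%, so a non-significant result must not be read as showing equal effects.

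### The stated within-gender power of 80% does not follow from its own inputs, which give 88%, and the overall and within-gender SDs do not fit the same 2% fall in both genders

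*Combined protocol and SAP*

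**What the plan says.** The Sample Size paragraph closes STATISTICAL PROCEDURES in the combined protocol and SAP. It makes two power statements in one sentence. The first covers the whole sample: "Sample size of 24 pairs has 88% power to detect a hepatic lipid change of 2% with a SD of 3" percent. The second covers men and women separately: "12 pairs of each gender has 80% power to detect this hepatic lipid change within gender group with a within-gender SD of 2" percent. Alpha is given as .05 for each, and the sentence ends "using a two-sided paired t-test".

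The planning values are said to come from the group's acromegaly treatment study. No mean change or SD by gender is shown. The section mentions multiple-comparison corrections only in general terms and does not tie them to this calculation. It gives no allowance for dropout.

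**The concern.** The second power statement supplies every input needed to check it, and the result is not the one printed. The paragraph also uses a smaller SD within gender than overall while keeping the same 2% change. A within-group SD falls below the pooled SD when the groups have different means, and the plan mentions no gender difference in response.

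At stake is how far a by-gender reading of the primary outcome, hepatic lipid, can be trusted. For a 2% fall in each gender, power is 88% if the SD is 2% and 56% if it is 3%. The reader is told 80% and cannot tell which SD the sponsor believes.

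**Working it through.** **Inputs, all from the Sample Size paragraph.** Change 2; SD of change 3 overall and 2 within gender; 24 pairs in total, 12 per gender; two-sided alpha .05; paired t-test. Power depends only on the ratio of change to SD, so the unit of the percentages does not matter.

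**Formula.** Noncentral t with df = n − 1 and noncentrality λ = (change / SD) × √n. Power is the probability of falling beyond ± the critical t value.

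**Step 1. Overall statement.** λ = (2/3) × √24 = 3.27, df = 23, critical value 2.07. Power = 87.8%. The stated 88% reproduces, so the method is the intended one.

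**Step 2. Within-gender statement.** λ = (2/2) × √12 = 3.46, df = 11, critical value 2.20. Power = 88.3%. The stated figure is 80%, about 8 points lower.

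**Step 3. What would give about 80%.** One input is changed at a time from n = 12, change 2, SD 2, two-sided alpha .05:

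| Change made | Power |
|---|---|
| Alpha .025 (.05 halved for two genders) | 79.3% |
| 10 pairs instead of 12 | 80.3% |
| SD 2.25 instead of 2 | 80.0% |
| Change 1.78 instead of 2 | 80.0% |

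Other methods at the stated n, change and SD also miss 80%: normal approximation 93.4%, one-sided t-test 94.5%, Wilcoxon (efficiency 0.864 to 0.955) 82.1% to 86.5%, two-sample formula 68.8%.

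**Step 4. Do the two SDs fit together?** For two equal groups with a common within-group SD:

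overall variance = within-gender variance + (half the gap between gender means)²

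- If both genders fall by 2 with SD 2, the gap is 0 and the overall SD is 2, not 3. Then 24 pairs would have 99.7% power.
- If the overall SD is 3 and the within-gender SD is 2, half the gap = √(9 − 4) = 2.24, so the gap is 4.47 points. Around an overall fall of 2, one gender changes by −2 + 2.24 = +0.24 and the other by −2 − 2.24 = −4.24. The power to detect those changes with 12 pairs each is about 7% and above 99.9%.

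**Step 5. Could rounding explain it?** An overall SD of 2.5 would print as 3, but 24 pairs would then have 96.3% power. A stated 88% (87.5% to 88.5%) with a change of 2 needs an overall SD of about 2.97 to 3.02. A stated 80% (79.5% to 80.5%) needs a within-gender SD of about 2.24 to 2.27. With 3 and 2.25, half the gap = √(9 − 5.06) = 1.98, so the gap is still about 4 points.

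Rounding of the change does not help either. If both powers are right as stated, SD/change is 3/2 = 1.5 overall and 2.25/2 = 1.125 within gender. Half the gap is then √(1.5² − 1.125²) = 0.99 times the overall change, which leaves one gender with almost no change.

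**Step 6. Within-gender power for a fall of 2 with 12 pairs, by common within-gender SD.**

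| SD | Power |
|---|---|
| 2 | 88.3% |
| 2.25 | 80.0% |
| 2.5 | 71.4% |
| 2.75 | 63.2% |
| 3 | 55.8% |

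At SD 3, 20 pairs per gender would be needed for 80%.

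**The case against.** **The wrong figure is secondary, and on its stated inputs it errs on the safe side.** This stands. The sample size rests on the overall statement, which is correct. Neither the hypotheses under Research Aims & Abstracts nor the outcomes and tests listed under STATISTICAL PROCEDURES include a by-gender comparison. Gender appears only in the eligibility list and in this power clause. A reader might infer that the trial is too small for its primary question, or that it commits to separate conclusions for men and women. The documents support neither.

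**The 80% may carry an unstated allowance for two tests or for dropout.** This is possible, but the sentence gives alpha as .05 and pairs as 12. An allowance for lost pairs would also sit oddly beside the overall figure, which uses all 24. It would be equally wrong to say that the figure must come from one particular changed input, because several give about 80%.

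**Each power statement is conditional and need not describe one joint scenario.** This stands in part. A within-gender SD below the overall SD is coherent if the genders differ in mean change, so it goes too far to say that the two SDs can never both hold. But the clause carries the same 2% change into each gender, and the difference needed to reconcile the SDs is about 4.5 points, more than twice the effect being planned for. An assumption of that size should be stated.

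**The 56% puts an SD of 3% into a clause that says 2%.** This also stands. A reader might take 56% as the real within-gender power or as the worst case, and it is neither. No document gives an SD of 3% within gender. With unequal SDs of 2 and 3.74, whose variances average (4 + 14)/2 = 9, power in the more variable gender would be 39%.

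**Conclusion.** The within-gender power is misstated: the plan's inputs give 88.3% against a printed 80%. This needs no assumption beyond the inputs and test the plan names.

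The overall SD of 3% and the within-gender SD of 2% do not fit one 2% fall in both genders. Assuming a 12/12 split and a common within-gender SD, they imply mean changes of about +0.2% and −4.2% around an overall fall of 2%. The plan does not state or justify such a difference, and rounding does not remove it. If the SD of 3% applied in each gender, power there would be 56%, as a scenario only.

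The overall statement of 24 pairs and 88% is sound. The point is a should-fix correction to a secondary power statement.

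**What to change.** 1. Restate the within-gender power as 88% for the stated inputs, or give the alpha, number of evaluable pairs or SD that yields 80%.
2. Make the two SDs coherent in one of three ways:
   - SD 3% throughout: overall 88%, within gender 56%.
   - SD 2% throughout: overall above 99%, within gender 88%.
   - Explicit mean changes and SDs for men and women, with their source in the preliminary data.
3. Note that the by-gender figure assumes 12 men and 12 women. The inclusion criteria admit both genders but set no number for either.

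The cost is rewording one paragraph, with no extra patients. The downside is a less favourable by-gender figure if SD 3% is kept.
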